3.2 Plain English Summary

Chest pain may be a symptom that is related to a narrowing of the heart blood vessels (coronary artery disease [CAD]). This chest pain, known as angina, can result in a reduced quality of life and, if not diagnosed and managed appropriately, could result in a heart attack. Coronary disease remains the largest cause of death in the United Kingdom today, with one death every 4 minutes. Guidelines recommend the use of tests to help diagnose and manage chest pain 'angina' patients. Coronary computed tomography angiography (CCTA) is a test that takes images of the heart blood vessels. It is the main test for patients presenting with angina, as it is excellent at saying when the heart blood vessels are normal and can be reassuring for patients. However, when narrowing's are present CCTA lacks the ability to tell whether they are causing the patient's symptoms.

A new technology, CT-derived fractional flow reserve (FFRCT) uses the CCTA images to make a 3D model of the heart blood vessels that shows whether there is a limitation in the blood flow to the heart which is causing the symptoms. The National Institute for Health and Care Excellence (NICE) recommends the use of FFRCT in a chest pain pathway. However, use of this new technology remains limited due to funding restrictions and uncertainty as to its benefit in the NHS.

This study aims to determine the extent to which the new FFRCT technology is safe and reliable, provides a quicker time to diagnosis for the patient, reduces the need for further tests and thus does the investment in the test represent good value to the NHS.

MRC

4 Introduction

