4.1 Background

The investigation of suspected stable coronary artery disease (CAD) should primarily be based on a non-invasive strategy (Knuuti *et al.*, 2020). In the United Kingdom Coronary Computed Tomography Angiography (CCTA) is now recommended as the first-line diagnostic test for patients with suspected angina and no prior CAD. (NICE, 2010) This recommendation by the National Institute for Health and Care Excellence (NICE) in 2016 was primarily driven by the very high sensitivity of CCTA to detect the presence or absence of coronary atheroma. (Nielsen et al., 2014; Meijboom et al., 2008) Given that the majority of patients with suspected angina turn out to have non-cardiac chest pain, and the majority of CCTA scans performed for this purpose show only minimal or no CAD, a significant proportion of patients can be immediately reassured by CCTA in the current NICE guidelines pathway. (Fordyce, Newby, & Douglas, 2016) However, in approximately a third of cases, CAD detected by CCTA is either indeterminate due to dense calcification or of intermediate severity which results in only modest specificity of CCTA to detect functionally significant 'ischaemic' CAD - and this remains its Achilles' heel. (Meijboom et al., 2008)

Recent advances in technology allow the use of raw CCTA images with computational fluid dynamic modelling to produce a 3D haemodynamic representation of the coronary tree flow limitation. (Lee et al., 2018) (Conte et al., 2017) (Taylor, Fonte, Min, City, & Angeles, 2013) This CT-Derived Fractional Flow Reserve (FFRCT) has developed rapidly since first concept and is now used in routine clinical practice. NICE, in a medical technology guidance (MTG 32), stated 'the clinical and cost effectiveness evidence justified FFRCT's use as a second line functional test for indeterminate or intermediate coronary stenoses'. The guidance also commented that 'based on the current evidence, using HeartFlow FFRCT may lead to cost savings of £214 per patient. By adopting this technology the NHS in England may save a minimum of £9.1 million by 2022 through avoiding invasive investigation and treatment'.

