NHS Digital's Data Access Request Service (DARS) will be queried to provide the patient episodes over the study period. NHSD collects national data sets containing details of all admissions, accident and emergency (A&E) attendances, and outpatient appointments at NHS hospitals in England. DARS will extract data from the following data sets:

- Emergency Care Data Set (ECDS)
- Hospital Episode Statistics Admitted Patient Care (HES APC)
- Hospital Episode Statistics Critical Care (HES CC)
- Hospital Episode Statistics Outpatients (HES OPC)
- Hospital Episode Statistics Accident and Emergency (HES AE)
- Diagnostic Imaging Dataset (DID)
- Medicines Dispensed in Primary Care Data Set (from NHS Business Authority)
- Civil Registration Deaths

These data sets will provide the following information:

- Patient demographics (such as age group, gender and ethnicity)
- Administrative information (such as dates and methods of admission and discharge)
- Geographical information; such as where patients are treated and the area where they live (post code).
- Medications (type, dose and whether processed)
- ICA and revascularisation data linked to patients.
- Incidence of downstream testing; stress echocardiograms, stress MRI or nuclear scintigraphy.

Costs will be calculated for all hospital attendances, diagnostic investigations and treatments from the published NHS England National Prices and Tariff workbook (2017-2019- HRG/OPEC codes) with the appropriate market forces factor applied. Health economic modelling will be performed by the University of Liverpool.

Referral to treatment (RTT) data is collected by each NHS trust for each patient. This data will be collected by the local research teams.

7 Study Population

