7.1 Setting and Target Population

The study population will include all patients that received a CCTA for symptoms suggestive of CAD at a participating institute, 12 months prior to the institutes first FFRCT study and up to 24 months

MRC

 $\mathcal{L}_{\mathcal{L}}$

FISH&CHIPS

following (total study period up to 36 months). The timeframe of study recruitment is dependent upon the starting time of each centre in the ITP programme. Centres that had a later start date (onboarding) will have a shorter recruitment period, with a minimum of 12 months. These centres represent the 'real-world' NHS hospitals that are a mixture of secondary and tertiary referral centres (not dedicated academic or research sites) with clinical experience in CCTA who have met the minimum quality standards set out by NHS England. Thus, the study population represents a true reflection of the current CCTA practice in the national population, reducing the potential effect of selection bias seen in many RCT's.

A study population of 85,292 patients received either CCTA analysis alone (standard of care group, n=75,361) or CCTA and Heartflow FFRCT analysis (FFRCT group, n=9,799) during the two years of the new technology being available to each site. The total study population over the 36 months is likely to be over 100,000.

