7.4 Follow up

Patient data will be collected up to a minimum of 24 months post-CCTA. Clinical data will also be analysed for the 6 months pre-CCTA to ensure no cross over between diagnostic pathways and prior testing (including CCTA) within 6 months (Figure 1).

Longitudinal long-term follow-up (>2 years) at 5 and 10 years would be feasible and cost effective using the same methodology of HES downloads and data analysis. This would provide a true long-term perspective of health care resource use in a stable angina population

Figure 1 Study Design Overview

8 Statistical Methodology

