8.2 Statistical Analysis

Analysis of the primary end-point is based on the rate of adverse events (MACE) as a composite of all-cause death, myocardial infarction and invasive coronary angiography without revascularization. Event rates over time will be calculated using Kaplan-Meier methodology from the time of the CCTA. Cox proportional hazard ratios will be used to determine the odds ratio (OR) of receiving revascularization post FFRCT compared to other tests.

Time to diagnosis will be compared using an 'intention to diagnose analysis' by analysing groups according to their investigative test (FFRCT vs CCTA alone).

The primary cost analysis will include total patient pathway costs at 12 months, with comparison between the two testing strategies. The mean cost difference with 95% confidence intervals and P value will be calculated. Sub-analysis will categorise the total costs breakdown as; Investigations, hospital stay, procedural costs.

Cost sensitivity analyses will be applied to the modelling, looking at different cost utilities in the UK and regional variability.

9 Good Clinical Practice

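### Section 8.2 has a Cox model yield an odds ratio for revascularisation, and leaves the clock and comparator for that by-test comparison unreconciled

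*Protocol*

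**What the plan says.** The protocol's Section 8.2 (Statistical Analysis) describes the event analysis in two consecutive sentences. The first sets the clock: "Event rates over time will be calculated using Kaplan-Meier methodology from the time of the CCTA". The second names the revascularisation analysis: "Cox proportional hazard ratios will be used to determine the odds ratio (OR) of receiving revascularization post FFRCT compared to other tests". It gives no time origin of its own and does not say which tests form the comparator. The next paragraph, on time to diagnosis, uses a different contrast, "analysing groups according to their investigative test (FFRCT vs CCTA alone").

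Other sections place the tests in time:

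- Section 7.4 counts follow-up from the CCTA: "Patient data will be collected up to a minimum of 24 months post-CCTA".
- Section 3.2 explains that FFRCT "uses the CCTA images to make a 3D model of the heart blood vessels", so it cannot precede the scan.
- Section 4.1 gives its place in the pathway: "use as a second line functional test for indeterminate or intermediate coronary stenoses".
- Section 6, in the list of information from the national data sets, treats the functional tests as later events too: "Incidence of downstream testing; stress echocardiograms, stress MRI or nuclear scintigraphy".
- Section 7.1 describes the groups by what patients received: "CCTA analysis alone (standard of care group, n=75,361) or CCTA and Heartflow FFRCT analysis (FFRCT group, n=9,799").

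**The concern.** There are two defects in one sentence.

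The first is the estimate. A Cox model compares instantaneous rates over follow-up and returns a hazard ratio. An odds ratio compares the odds of having had the event by a fixed time and needs a binary model. A reader told that the reported figure is an odds ratio would convert it to risks wrongly, by more as revascularisation becomes more frequent.

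The second is time zero. If the Cox model uses the stated origin, group membership is decided by something that happens after the clock starts. A patient can be counted as FFRCT only after remaining free of the event until the FFRCT, and that waiting time is credited to the FFRCT group. Patients in a functional-test group must likewise remain event-free until their own test. The protocol states no landmark, no time-updated exposure and no separate origin for the Cox model.

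Section 4.2 presents fewer unproductive angiograms and a higher revascularisation rate among those sent for angiography as part of the case for FFRCT. A revascularisation ratio from this study would therefore be read as evidence of efficiency.

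**Working it through.** The plan gives no revascularisation rate, effect size or CCTA-to-test interval, so there is no figure of its own to reproduce. All rates and delays below are assumptions.

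**Step 1: hazard ratio against odds ratio.** With reference risk p0 and proportional hazards, p1 = 1 − (1 − p0)^HR and OR = [p1/(1 − p1)] / [p0/(1 − p0)]. For HR = 2 this reduces to OR = (2 − p0)/(1 − p0).

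| Assumed p0 | OR when HR = 2.0 | Excess of OR over HR | OR when HR = 1.5 |
|---|---|---|---|
| 1% | 1.99/0.99 = 2.01 | 0.5% | 1.50 |
| 10% | 1.90/0.90 = 2.11 | 5.6% | 1.54 |
| 20% | 1.80/0.80 = 2.25 | 12.5% | 1.59 |
| 30% | 1.70/0.70 = 2.43 | 21% | 1.65 |
| 40% | 1.60/0.60 = 2.67 | 33% | 1.73 |

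The same relation can be run from risks, with HR = ln(1 − p1)/ln(1 − p0):

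- 30% against 15%: HR = 2.19, OR = 2.43.
- 50% against 25%: HR = 2.41, OR = 3.00.

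**Step 2: order of events.** The CCTA starts the clock (8.2) and follow-up (7.4). FFRCT is computed from that scan (3.2) and is second-line (4.1). The functional tests are downstream of it (6). Membership of either tested group is therefore unknown at time zero.

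**Step 3: what that does when there is no true effect.** A simulation used 400,000 patients per scenario and a true hazard ratio of 1. The share intended for FFRCT was 9,799/(75,361 + 9,799) = 11.5%, from Section 7.1. Assumed inputs were 12-month risks of 10%, 20% and 30%, a constant or front-loaded hazard, exponential delay from CCTA to test, and 24 months of follow-up. A Cox model was fitted with the clock at the CCTA and the group fixed by test received.

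FFRCT against everyone else:

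| Mean delay to FFRCT | Apparent HR (truth 1) |
|---|---|
| 7 days | 0.95 to 1.00 |
| 30 days | 0.86 to 0.96 |
| 60 days | 0.80 to 0.90 |
| 90 days | 0.74 to 0.86 |

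FFRCT at a mean of 7 days against other second-line tests at means of 7 to 90 days, untested patients excluded: apparent HR 0.99 to 1.25. When both delays are 7 days the true answer is exactly 1 by symmetry and the runs gave 0.99 to 1.04, so departures of a few percent are simulation noise.

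The bias thus runs below 1 against everyone else, at or above 1 against later functional tests, and shrinks towards nothing when the delay is short.

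**The case against.** The strongest reply is that the first defect is a slip of label. The method named is Cox, the output will be a hazard ratio, and changing two words repairs it. Revascularisation is also not among the primary endpoints in Section 5.3. Both points stand, and they limit the weight of the finding. They do not make the sentence correct, and a later analysis plan would not cure a protocol that fixes a method and names the wrong output.

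On time zero, the reply is that the CCTA origin belongs to the Kaplan-Meier sentence, and that the Cox sentence, which speaks of revascularisation after FFRCT, may intend a clock starting at the FFRCT. That is possible, so the immortal-time concern is an inference. But on that reading patients with CCTA alone have no corresponding start date, so the passage needs reconciling either way. Landmarks and time-updated exposure are often left to an analysis plan, which may exist.

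Three stronger readings are tempting but unsupported:

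- That FFRCT revascularisation would be understated by a definite amount, such as 5% to 20%. Such a figure only restates an assumed share of events falling in the waiting period, and the direction can reverse.
- That anyone revascularised first must land in the comparator. This fits CCTA alone. If the comparator is the functional tests, a patient revascularised before any second test is in neither group.
- That revascularisation is known to be common. The comparison covers everyone tested, not only those with a positive result, and no rate is given.

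**Conclusion.** The point holds in two parts of unequal certainty.

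It is certain from the text that Section 8.2 attaches an odds ratio to a model that estimates a hazard ratio. For a hazard ratio of 2.0, the misreading is under 1% at 1% reference risk, about 5% to 6% at 10%, and 12% to 33% at 20% to 40%. This assumes proportional hazards and rates that the protocol does not supply.

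It is a reasonable inference, not a demonstrated fault, that the by-test comparison is exposed to immortal-time bias. This rests on the Cox model using the only stated origin and on groups being fixed by test received. Neither size nor direction can be determined without the CCTA-to-test intervals and a named comparator. The comparator is itself unsettled, since Section 8.2 refers to other tests for revascularisation and to CCTA alone for time to diagnosis.

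A reader might also infer that death must be handled as a competing event. That is an analytical preference and not part of this finding. The correction should be made, but no listed primary endpoint depends on this sentence.

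**What to change.** Amend the revascularisation sentence in Section 8.2 to do three things:

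1. Call the Cox estimate a hazard ratio. If an odds ratio is wanted, obtain it by logistic regression of revascularisation within a fixed 12 months of the CCTA.
2. Name the comparator: the other second-line tests, CCTA alone, or each in a separate analysis.
3. State the time origin. For any comparison by test received, either start all groups at a common landmark after the CCTA, or treat the test as a time-updated exposure, with patients unexposed until its date.

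The cost is a few lines of text and slightly more programming. A landmark also drops patients with earlier events, so its timing should be fixed in advance. The one practical dependency is test dates. Section 6 lists the Diagnostic Imaging Dataset and FFRCT-specific data from the provider as sources, but mentions dates only for admission and discharge. The sponsor should confirm that dates of FFRCT and of the functional tests are available before committing to either approach.

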5.4.2 Imaging biomarkers

Using the list of CCTA originally provided by the sites, the participating centres PACS teams will send the anonymised CCTA datasets to the CTU data storage for future linkage to the outcome data provided by NHS Digital. This process will ensure that anonymity is preserved while providing for a valuable resource in terms of a large database of anonymised imaging datasets with outcome data. There will also be the opportunity to repeat the data capture from NHS Digital in future years to establish medium and long-term outcomes. The purpose of creating this repository of anonymised outcome and imaging data is to allow for future research projects into image analysis of CTA including deep learning algorithms, radiomics analysis, and biomechanical modelling of coronary arteries all with the goal to improving future risk stratification to better target therapeutic interventions.

6 Study Design

This is a multi-centre, retrospective, observational analytic cohort study design.

This pragmatic 'real-world' trial, is designed to utilise big data to answer practical health questions and determine clinical outcomes in a timely fashion. Randomized clinical trials (RCT's) in comparative effectiveness research (CER) have been considered the gold standard. These are however, subject to several problems, including cost, patient selection bias and slow translation of knowledge into practice. (Angus, 2015) This study design removes any patient treatment heterogeneity effect seen in RCT's by assessing the impact of a new intervention on a whole population. (Longford, 1999) by utilising the electronic health record (EHR) data already collected by the NHS. This trial will thus represent a true assessment of the effectiveness of a new health technology on a population basis in the current NHS system and will enable the rapid translation of research into clinical and health care policy decisions.

Participants will include all individuals who had a CCTA performed at an institute participating in the NHSE FFRCT ITP during 2018-2020. All CCTA 12 months prior to and up to 24 months following the

FISH&CHIPS

Medical Research Council

start of a FFRCT programme (total study period 36 months) will be assessed. The cohort from this population that received an FFRCT will be separately identified, with linkage to the NHS digital data outcomes. HeartFlow will provide FFRCT-specific data.

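### The time-to-diagnosis analysis is labelled 'intention to diagnose' but groups patients by test, apparently the test received, so scans submitted for FFRCT without a result would drop out of the FFRCT group.

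*Protocol*

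**What the plan says.** Section 8.2 gives the rule for one endpoint, time to diagnosis. It names an 'intention to diagnose' analysis, to be done "by analysing groups according to their investigative test (FFRCT vs CCTA alone"). The MACE and cost paragraphs of the same section do not use the intention label. The cost paragraph compares two testing strategies and gives no rule for allocating patients to them.

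Two other places describe the groups. Section 7.1 says that patients "received either CCTA analysis alone (standard of care group, n=75,361) or CCTA and Heartflow FFRCT analysis (FFRCT group, n=9,799"). Section 6 says: "The cohort from this population that received an FFRCT will be separately identified". Section 6 also names the source of the FFRCT information: "HeartFlow will provide FFRCT-specific data".

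The protocol does not mention scans that were submitted for FFRCT but rejected or not analysable.

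**The concern.** An intention-to-diagnose analysis keeps a patient with the test that was ordered, whether or not the test gave a result. Grouping by the test obtained is a different analysis, because membership of the FFRCT group then depends on FFRCT having worked. A patient whose submitted scan gives no result probably still needs another test and waits longer for a diagnosis. Leaving such patients out makes FFRCT time to diagnosis look shorter than it would be for everyone sent for the test.

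Adjusting for CCTA severity would not repair this. Of two patients with the same CCTA findings, both submitted, only the one with a result would be counted under FFRCT.

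Time to diagnosis is a primary endpoint in section 5.3. Downstream testing is open to the same bias if it is compared by test, and section 5.3 points that way by counting tests after the index FFRCT.

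**Working it through.** **Do the group counts close?** Section 7.1 gives a total of 85,292 and groups of 75,361 and 9,799.

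- 75,361 + 9,799 = 85,160
- 85,292 − 85,160 = 132 (0.15% of the total) in neither stated group

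The protocol does not say who the 132 are. If all were failed submissions, the failure share would be 132/(9,799 + 132) = 1.3%. They would then be missing from the FFRCT group without entering the comparator.

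**How many patients could move?** The protocol gives no failure rate, so the share f of submissions without a result is assumed. Take 9,799 as completed analyses and suppose that failures sit within the 75,361. Then failures = 9,799 × f/(1 − f).

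| f (assumed) | Failures | Share of 75,361 |
|---|---|---|
| 2% | 200 | 0.27% |
| 5% | 516 | 0.68% |
| 10% | 1,089 | 1.44% |

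**Effect on time to diagnosis.** Suppose failures take D days longer than the other patients in either group. Leaving them out lowers the FFRCT mean by f × D. Placing them in CCTA alone raises that mean by (failures/75,361) × D. For an assumed D = 30 days:

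| f | FFRCT mean too low by | Comparator mean too high by | Ratio |
|---|---|---|---|
| 2% | 0.6 days | 0.08 days | 7.5 |
| 5% | 1.5 days | 0.21 days | 7.3 |
| 10% | 3.0 days | 0.43 days | 6.9 |

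The ratio does not depend on D. About seven-eighths of the bias comes from the FFRCT side.

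**Effect on downstream testing, if compared by test.** Assume 10 tests per 100 in analysed patients and 60 to 90 per 100 in failures. With failures included, the FFRCT rate is 10 + f × (60 to 90 − 10) per 100:

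- f = 2%: 11.0 to 11.6
- f = 5%: 12.5 to 14.0
- f = 10%: 15.0 to 18.0

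The FFRCT rate would be understated by 1 to 8 tests per 100. If the other comparator patients also have 10 per 100, the net rise in the comparator is failures × (60 to 90 − 10)/75,361. That runs from 200 × 50/75,361 = 0.13 to 1,089 × 80/75,361 = 1.16 per 100.

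**The case against.** The strongest reply is that the protocol never says where an unanalysable scan goes. Under an intention label, the investigative test could mean the test requested, and 9,799 could already count submissions. If so, the rule is sound and only the wording is loose. This stands as far as it goes: a reader might infer that the protocol assigns failures to CCTA alone, but no section states it, and the 132 unallocated patients show that the two groups do not exhaust the population. It does not remove the point. Sections 6 and 7.1 both speak of FFRCT received, and nothing keeps a failed submission with FFRCT.

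Scope is the second reply, and it also stands. The quoted rule covers time to diagnosis only. A reader might extend the bias to cost, but section 8.2 gives no allocation rule there. Section 4.2 describes the cost comparison as one of pathways, with FFRCT used selectively, and in such a comparison failed scans would stay on the FFRCT side.

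Three further inferences are not supported:

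- That FFRCT's failures are mainly a burden on the comparator. They would be at most 1.44% of it over the assumed range.
- That failures are mostly densely calcified scans. Section 4.1 says that calcification makes CCTA indeterminate; it does not say why an FFRCT analysis fails.
- That a failure-rate endpoint has been promised. The plain English summary says "This study aims to determine the extent to which the new FFRCT technology is safe and reliable", but the formal objective and endpoints do not. Adding one is a preference.

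Finally, detailed handling of unanalysable scans is often left to the SAP, which is not shown. Here, however, the protocol itself states a grouping rule that does not match its label.

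**Conclusion.** The point holds for time to diagnosis, and conditionally for downstream testing. The label and the grouping rule in section 8.2 conflict, and sections 6 and 7.1 favour reading the rule as test received. Followed that way, the plan removes submitted scans without a result from the FFRCT group and flatters that group.

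The size cannot be determined from the protocol. The failure share, the 30-day delay and the test rates used above are all assumptions. The direction rests on failed patients waiting longer or having more tests than those with a result. If 9,799 already counts submissions, the bias is absent and a clarifying sentence is enough. The change should be made, but it does not undermine the study as a whole.

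**What to change.** - In sections 7.1 and 8.2, define the FFRCT group for any by-test comparison as every CCTA submitted for FFRCT, with or without a result. Align the sentence in section 6.
- State whether 9,799 counts submissions or completed analyses, and who the 132 patients are.
- Request submission date and result status with the vendor's FFRCT data. The protocol does not say whether those data include failed submissions, so the sponsor should confirm that they are available.
- Keep the completed-analysis group as a sensitivity analysis.

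The cost is a small addition to the data request (submission date and result status), revised wording, and probably a slightly less favourable FFRCT result.

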5.1 Primary objective

The study aims to identify differences in health-related events, time to diagnosis and overall costs in a clinical population undergoing CCTA and FFR_{CT} for symptoms suggestive of stable CAD, compared to a previous 'standard of care' diagnostic chest pain pathway.

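### Section 7.1 defines the study groups by test received while FFRCT was available, so they do not match the objective's comparison with the previous pathway and differ in disease severity

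*Protocol*

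**What the plan says.** **The question.** Section 5.1 sets the FFRCT population "compared to a previous 'standard of care' diagnostic chest pain pathway". Section 4.2 frames the cost question as one pathway with selective FFRCT against a standard-of-care pathway. The hypothesis in section 3.1 is about adding FFRCT to a CCTA pathway.

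**The data.** Section 6 takes in "All CCTA 12 months prior to and up to 24 months following the" start of a site's FFRCT programme, and section 7.1 repeats this. A cohort from before FFRCT is therefore already in the study.

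**The groups.** Section 7.1 says patients "received either CCTA analysis alone (standard of care group, n=75,361) or CCTA and Heartflow FFRCT analysis (FFRCT group, n=9,799"), and that this was "during the two years of the new technology being available to each site". These are the only groups the protocol defines and counts.

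**The analysis.** Section 8.2 compares time to diagnosis under an intention-to-diagnose label, by "analysing groups according to their investigative test (FFRCT vs CCTA alone"). It sets revascularisation after FFRCT against other tests. For cost it refers only to two testing strategies, and for MACE it states no grouping.

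**Who gets FFRCT.** Section 4.1 cites guidance supporting its "use as a second line functional test for indeterminate or intermediate coronary stenoses", and says that most CCTAs done for suspected angina show minimal or no disease.

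**The concern.** Membership of the FFRCT group depends on what the CCTA showed. A patient reassured by a normal scan stays in CCTA alone, and is likely to have a short time to diagnosis, few further tests, low cost and low risk. A patient with an uncertain stenosis is the one considered for FFRCT. A contrast between these groups mixes any effect of FFRCT with the reason it was requested.

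Both groups in section 7.1 also come from the period when FFRCT was on offer, so neither is the previous pathway named in the objective. The intention-to-diagnose label does not fit either. An intention-based analysis would keep patients in the strategy open to them at the CCTA; grouping by the test actually done is an as-tested analysis.

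At stake is whether the main results can be read as the effect of adding FFRCT to the pathway, including the claim that doing so is safe.

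**Working it through.** The protocol states no effect size or power to reproduce. The check asks what the section 7.1 groups would show if FFRCT had **no effect at all**.

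**Inputs**
- Group sizes (7.1): 75,361 and 9,799, summing to 85,160. The text gives 85,292, which is 132 more; this does not matter here.
- Disease mix at CCTA (8.1): 37% normal, 38% non-obstructive, 25% obstructive.
- Annual event rates (8.1): 0.31% normal, 2.06% obstructive. The non-obstructive rate *x* is not given; it is assumed to lie between 0.31% and 2.06%.
- Event rate in a registry of FFRCT-tested patients (8.1): 1.16% at one year.
- The severity mix of FFRCT recipients is not given, so several mixes are assumed.

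**Composition.** If no FFRCT recipient has normal arteries, the normal share of CCTA alone is 0.37 × 85,160 / 75,361 = 31,509 / 75,361 = 41.8%, against 0% of the FFRCT group.

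**Event rates.** The overall rate is r = 0.37 × 0.31 + 0.38x + 0.25 × 2.06 (in %), which is 0.7475%, 1.0705% and 1.4125% for x = 0.31%, 1.16% and 2.06%. With r_F the rate in FFRCT recipients, the CCTA-alone rate is

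r_C = (85,160 r − 9,799 r_F) / 75,361.

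Example, all recipients obstructive, x = 0.31%: r_C = (85,160 × 0.7475 − 9,799 × 2.06) / 75,361 = 0.577%, so the ratio is 2.06 / 0.577 = 3.57.

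| Assumed FFRCT recipients | x = 0.31% | x = 1.16% | x = 2.06% |
|---|---|---|---|
| All obstructive | 3.57 | 2.19 | 1.55 |
| Half obstructive, half non-obstructive | 1.72 | 1.61 | 1.55 |
| Diseased patients in proportion 38:25 | 1.41 | 1.50 | 1.55 |
| All non-obstructive | 0.39 | 1.10 | 1.55 |
| Unselected | 1.00 | 1.00 | 1.00 |

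In the 38:25 row, the chance that this purely spurious difference reaches two-sided p < 0.05 (level assumed) is 85% to over 99%.

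**Using the 1.16% rate as r_F.** For x = 0.31%, 1.0% and 2.06%, r_C is 0.69%, 0.99% and 1.45%, giving ratios of 1.67, 1.17 and 0.80. The last needs care: with x = 2.06%, a rate of 1.16% implies (2.06 − 1.16) / (2.06 − 0.31) = 51% of recipients with normal arteries, which sits badly with second-line use. The registry may also count events differently.

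**Grouping by availability.** With stable case mix and no effect, patients before and after a site's first FFRCT share the same expected rate r, so the ratio is 1.00. The price is dilution. Uptake is 9,799 / 85,160 = 11.5%, and 1 / 0.115 ≈ 8.7. Assume a pre-period of 100,000 − 85,292 = 14,708 patients (the text says only that the total is likely over 100,000), 80% power and two-sided 5%. The detectable difference is 2.80 × √[r(1 − r)(1/14,708 + 1/85,292)], which is 0.22 percentage points at r = 0.75% and 0.26 at r = 1.07%. Multiplied by 8.7, this is about 1.9 to 2.2 points per FFRCT recipient.

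**The case against.** **Scope.** A reader might infer that section 8.2 analyses every endpoint by test received. It does not say so. The sentence on investigative test governs time to diagnosis; revascularisation follows a similar split. For cost, the two testing strategies could be the two pathways of section 4.2. The group sizes in section 7.1 may partly be a report of volumes, and the figure with the design overview is not available in the text reviewed. This stands as a limit: for MACE and cost, the point rests on section 7.1 giving the only defined groups, with nothing in the available text making before versus after primary.

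**Direction.** A reader might infer that the bias must make FFRCT look harmful, with ratios of 1.5 to 3.6. That requires recipients to be wholly or half obstructive, which the documents do not say; indeterminate or intermediate stenosis points to a mixed group. Ratios below 1 also arise. Moreover, the MACE composite in section 8.2 includes angiography without revascularisation, and the rates in section 8.1 are not said to include it.

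**Adjustment.** A reader might infer that no covariate adjustment could repair the comparison. That is too strong. The NHS data items listed in section 6 contain no stenosis grade, but section 5.4.2 plans to link CCTA images to outcomes, albeit for future research, and an unseen SAP may specify adjustment. What stands is that severity adjustment cannot be presumed.

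**The alternative is not free.** A before-and-after comparison is open to calendar-time trends, and the detectable effect per recipient is about as large as the whole 2.06% obstructive rate. Both objections stand and belong in the fix. Neither makes the as-tested groups answer the stated question.

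**Conclusion.** The point holds. The protocol asks about pathways and collects the cohort needed to answer, but defines its groups by test received within the availability period and applies an as-tested split explicitly to time to diagnosis and in similar terms to revascularisation. For MACE and cost the comparison is left unstated, with those same groups as the only ones defined. Because FFRCT is chosen after the CCTA result, the groups differ in severity, and endpoint differences would be expected without any FFRCT effect.

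The size and direction are not established. With no effect, illustrative event-rate ratios span about 0.4 to 3.6, or about 0.8 to 1.7 with the protocol's 1.16% rate. These rest on an assumed severity mix and an unstated non-obstructive rate; they show the mechanism and are not predictions. The conclusion itself needs only the second-line role of FFRCT stated in section 4.1. Since it decides whether the main results can be interpreted, it should be settled before analysis.

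**What to change.** In sections 7.1 and 8.2:

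- State for each endpoint that the primary comparison is all eligible CCTA patients before, versus all eligible CCTA patients after, each site's first FFRCT, whether or not FFRCT was done.
- Stratify by site and adjust for calendar time as far as the actual spread of start dates allows. Section 7.2.1 gives an eligibility window of April 2018 to March 2020, not the spread achieved; if starts cluster, availability and calendar time will be hard to separate, and the protocol should say so.
- Remove the grouping by investigative test from the primary analysis, or rename it as-tested.
- Keep FFRCT versus CCTA alone as a secondary comparison, labelled as confounded by severity unless restricted to, or adjusted for, comparable CCTA findings.
- If an effect per FFRCT recipient is obtained by scaling for uptake, state the assumption that availability acts only through FFRCT and does not change who is referred for CCTA.

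**Cost.** Wording in two protocol sections and matching SAP text; no new data, because the pre-programme cohort is already included. The real price is precision: at 11.5% uptake the effect per CCTA patient is about one ninth of that per recipient. The protocol should state that precision for rare safety events is limited.
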